#### 4 STUDY POPULATION AND STUDY PROCEDURES

#### 4.1 Inclusion and exclusion criteria, justification of study population

The study population will consist of male or female patients identified by GPs who meet the following **inclusion criteria**:

- Aged 65 or older
- Resident in the Lugano municipality
- Having access to a GP
- Diagnosed for at least six months with one or more of the following lifestyle-related pathological conditions:
  - o Obesity (BMI ≥30)
  - Obstructive sleep apnea syndrome
  - Type 2 Diabetes Mellitus
  - Chronic Obstructive Pulmonary Disease (COPD) (GOLD 2 or higher)
  - Uncontrolled hypertension
  - Uncontrolled gouty arthritis
  - Metabolic dysfunction and alcohol-related liver disease (MetALD)

To ensure consistency in participant selection, individuals must have a confirmed diagnosis that meets these criteria. No specific treatment regimen or symptom severity threshold is required (except for COPD, since GOLD1 is asymptomatic).

## The GP will assess the appropriateness of participation based on the individual's clinical profile.

We also envisioned a number of **exclusion criteria** to ensure the appropriateness of participant selection and the feasibility of the intervention. We will exclude:

- Individuals who are still in employment (as the study focuses on retirees). Those who
  undertake occasional freelance work or small consultancies (e.g., fewer than 8 hours per
  week) may still be eligible, provided their professional activities do not interfere with
  participation in the study.
- Individuals with diagnosed moderate to severe dementia or cognitive impairment that affects their ability to provide informed consent
- Individuals with significant mobility restrictions that would prevent engagement in artistic and cultural activities (unless safe accommodations can be arranged)

These criteria ensure that the study includes individuals who can actively participate in cultural prescribing interventions while considering medical appropriateness and potential barriers to engagement.

[figure not shown]
#### 4.2 Recruitment, screening and informed consent procedure

The recruitment process will follow a number of steps (see Figure 1). Patients will be screened by their general practitioners (GPs) during routine appointments to confirm eligibility. Access to a GP is a prerequisite for inclusion in the study. To facilitate this process, the research team will provide GPs with a **structured screening form** (see the document "Formulario reclutamento") to assess whether patients meet the inclusion criteria. Along with the screening form, GPs will receive a **standardized gridline** (see the document "Griglia introduzione studio") to help introduce the study to the patient in a consistent and clear manner. If a patient is deemed eligible and expresses interest in participating, the GP will forward their contact details to the **research team at the Institute of Family Medicine** using the structured screening form.

Once referred, potential participants will be contacted over the phone to **confirm interest and schedule the baseline assessment**. Within three days from this phone call, potential participants will receive a written confirmation of their appointment (date, time, and address) and an **information sheet at home**, including a study description and a copy of the consent form (see document *ICF*), allowing them to review the materials before their baseline assessment.

GPs will **not** be responsible for handling consent forms but will collect and document key recruitment data, including the total number of individuals screened and those invited to participate, through a structured form provided by the research team (see the document "Rapporto screening"). This information will help estimate eligibility rates, assess recruitment efficiency, and inform planning for a larger-scale randomized controlled trial (RCT).

Figure 1. Recruitment process

The research team at the Institute of Family Medicine at the Ospedale Italiano in Lugano will manage the collection of consent forms during the baseline assessment, ensuring that participants fully understand the study before signing and before any study-related procedures. Participants will be asked if they have any questions before signing the document. The investigators will explain to each participant the nature of the study, its purpose, the procedures involved, the expected duration, the potential risks and benefits and any discomfort it may entail. Each participant will be informed that the participation in the study is voluntary and that he or she may withdraw from the study at any time and that withdrawal of consent will not affect his or her subsequent medical assistance and treatment.

The participant will be informed that his or her medical records may be examined by authorised individuals other than their treating physician. All participants for the study will be provided a participant information sheet and a consent form describing the study and providing sufficient information for participant to make an informed decision about their participation in the study (at least one week). The formal consent of a participant, using the approved consent form, will be obtained before the participant is submitted to any study procedure. The consent form will be signed and dated by the investigator or his designee at the same time as the participant sign. A copy of the signed informed consent will be given to the study participant. The consent form will be retained as part of the study records.

The first study participant will be included in the trial within two months following the issuance of the authorization by the Ethics Committee. The investigator or the sponsor notifies the Ethics Committee of the first study participant, in accordance with art 62 lit. c ClinO, resp. art 38 ClinO.

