	interventions that are more inclusive and effective for different groups. To achieve this, we will aim for a balanced sample with a 50:50 gender distribution. Gender will be integrated into the analysis to identify any differences in engagement or outcomes, ensuring that the interventions are appropriately adapted for all participants.  The study's minimal risks are outweighed by the potential benefits of enhanced mental health				
Risk / Benefit Assessment	and well-being, social connection, and improved health outcomes through engagement in artistic and cultural prescriptions.				
Objective(s)	Primary objective: Explore programme feasibility and acceptability by assessing programme uptake, attendance rates, reasons for non-attendance, and barriers to engagement.  Secondary objectives: Test whether there is any indication of an improvement in health orientation; compare health orientation and health outcomes of those participating in the programme versus the control group.				
Endpoint(s)	Primary endpoints: Uptake and feasibility of recruitment and research procedures. Secondary endpoints: Health Orientation, Mental health and well-being, physiological measures, consultations and hospitalizations/emergency department accesses.				
Study Design	Double-arm feasibility study with a control group, incorporating baseline and post-intervention assessments.				
Inclusion- / Exclusion Criteria	The study population will consist of male and female patients identified by general practitioners who meet the following inclusion criteria:  • Aged 65 or older  • Resident in the Lugano municipality  • Having access to a GP  • Diagnosed > six months with one or more of the following pathological conditions:  Obesity (BMI ≥30); Obstructive sleep apnea syndrome; Type 2 Diabetes Mellitus; Chronic Obstructive Pulmonary Disease (COPD) (GOLD 2 or higher); Uncontrolled hypertension; Uncontrolled gouty arthritis; Metabolic dysfunction and alcohol-related liver disease (MetALD). We will exclude:				

	
 
Individuals who are still in employment (as the study focuses on retirees). Those who undertake occasional freelance work or small consultancies (e.g., fewer than 8 hours per week) may still be eligible, provided their professional activities do not interfere with participation in the study.
 
Individuals diagnosed with moderate to severe dementia or cognitive impairment that affects their ability to provide informed consent.
 

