#### Consultations and hospitalisations/emergency department accesses

We will administer a short questionnaire to the participant's general practitioner (GP) to collect additional data on the participant following the last follow-up (see the document "Questionario medici"). The questionnaire will include questions regarding the frequency of consultations with the GP in the year prior to the study and since its initiation, as well as the numer of hospitalizations or emergency department accesses before and after intervention. The GP will complete the questionnaire and return it to us by email or using a pre-stamped, self-addressed envelope.

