Participants will be required to attend all assessments at the Family Medicine Service of the **Ospedale Italiano in Lugano**. Questionnaires will be completed using a tablet. **Nurses and physicians** holding a GCP certificate will be responsible for conducting blood draws, reviewing medications, and overseeing the proper use of wearable devices.

Approximately 3 months will be allocated for recruiting participants, during which general practitioners (GPs) will screen potential candidates for eligibility.

Each participant will be involved in the study for 13 months, which includes:

- 1 month for baseline assessment and assignment to a cultural or artistic activity.
- 6 months for participation in the cultural or artistic activity.
- 6 months of follow-up assessments and optional interviews.

Blood will be collected at baseline, at the 6-month follow-up, and at the 12-month follow-up. The blood samples will be used to measure relevant health markers as part of the study's secondary objectives. Blood samples will be stored securely at the Ospedale Italiano and anonymized with unique participant codes.

Efforts to recruit a diverse sample through multiple GP practices in the Lugano municipality will help mitigate selection bias. To address attrition, participants will be encouraged to attend all study assessments through clear communication and regular follow-up by the research team. Additionally, dropout reasons will be monitored and recorded to help assess and adjust for this bias in the analysis. Standardized protocols for data collection and use of validated tools (questionnaires, devices) will minimize measurement bias. Regular calibration and monitoring of devices will ensure accuracy. Key factors such as sex, gender, age, and pre-existing health conditions will be controlled for in the analysis by matching participants for these variables in the experimental and control groups. Additionally, the study will take into account potential confounding factors by adjusting for them in the statistical analysis models.

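### Because patients are found at a GP appointment, the within-arm before-after change in GP consultations is open to a selection artefact; the between-arm difference in change should be the result for this endpoint.

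*Protocol*

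**What the plan says.** **Entry.** Protocol section 4.2 states "Patients will be screened by their general practitioners (GPs) during routine appointments to confirm eligibility", and section 4.1 likewise has patients identified by GPs. No other route is described. Consent comes later: section 4.2 says the hospital research team "will manage the collection of consent forms during the baseline assessment". Section 4.3 gives the time frame: "Approximately 3 months will be allocated for recruiting participants".

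**Outcome.** The synopsis lists "Secondary endpoints: Health Orientation, Mental health and well-being, physiological measures, consultations and hospitalizations/emergency department accesses". Section 3.2 says a questionnaire goes to the GP "to collect additional data on the participant following the last follow-up". It asks for "the frequency of consultations with the GP in the year prior to the study and since its initiation", and for "hospitalizations or emergency department accesses before and after intervention". The two counts thus have differently worded reference points. Neither is tied to a date, and the handling of the screening appointment is not mentioned.

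**Analysis.** The synopsis (Statistical Considerations) names paired t-tests, linear mixed-effects models or repeated-measures ANOVA for primary and secondary outcomes. Section 5.1 puts paired t-tests first for judging the impact of the intervention and says the other models may be applied. Section 3.1 sets comparison with the control group as a secondary objective. Section 3.3 plans 80 programme and 20 control participants.

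**The concern.** A person who enters through a GP visit has, by construction, at least one visit close to entry. If the before-year ends at that person's baseline, this visit falls in the before-count. If the study is taken to begin on a calendar date when recruitment opens, it falls in the after-count. Either way the two windows are not exchangeable even when nobody's use of the GP changes, and a paired test on one arm cannot separate this from an effect of the programme.

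At stake is a reported change in GP use, attributed to cultural prescribing, that recruitment alone could produce. The count is collected once, after the last follow-up. If the form asks for totals only, the analysis cannot undo the problem later.

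**Working it through.** **Inputs from the protocol.** 80 + 20 = 100 participants; a recruitment window of about 3 months (w = 0.25 year); 1 + 6 + 6 = 13 months per participant; significance at p<0.05, taken as two-sided. Both sums agree with the text. The protocol gives no visit rate, SD or effect size, so it has no figure of its own to reproduce for this endpoint.

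**Assumed, not in the protocol.** A steady personal rate of m = 3 to 12 GP visits a year, no true change, and either random (Poisson) or regularly scheduled visits.

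**1. Entry at a randomly chosen visit, windows of 12 months split at baseline.** Expected before-count m + 1, after-count m, so the change is -1.0. The standard error of the mean change in 80 people is √(2m/80). For m = 4 this is 0.316, and 1/0.316 = 3.16; the chance of a false positive is about Φ(3.16 - 1.96) = 89%. The same steps give 73%, 61% and 45% for m = 6, 8 and 12.

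**2. Entry at the first visit in the 3-month window, random visits.** The stretch from the opening of recruitment to that visit is visit-free and offsets part of the excess. With V the time to that visit, the change is -1 + m·E(V | V < w) = -mw/(e^(mw) - 1).

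| m per year | mw | False change | Simulated paired-t false positives, n = 80 |
|---|---|---|---|
| 3 | 0.75 | -0.67 | 69% |
| 4 | 1.0 | -0.58 | 45% |
| 6 | 1.5 | -0.43 | 19% |
| 8 | 2.0 | -0.31 | 12% |
| 12 | 3.0 | -0.16 | 7% |

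The simulation gave the same changes within sampling error (-0.67, -0.58, -0.43, -0.34, -0.21). At n = 20 false positives ran from 22% down to 5%.

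**3. Regular visits (simulation).** -0.11 to -0.15 visit when everyone shares one rate; -0.2 to -0.7 when rates differ between people. Rejection rates are not informative here, because near-deterministic counts have almost no variance.

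**4. Other readings of the windows.** With a 13-month after-period and raw counts, case 2 becomes m/12 - mw/(e^(mw) - 1): -0.42 at m = 3, +0.07 at m = 6, +0.84 at m = 12. Across all scenarios the range is about -0.4 to +0.9. With a calendar start and annualised counts, the simulation gave +0.15 to +0.55 for random visits and about -0.1 to +0.3 for regular ones.

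**5. Leaving out only the screening visit.** If the before-year ends the day before that visit, case 2 becomes 1 - mw/(e^(mw) - 1): +0.42, +0.57, +0.69 and +0.84 at m = 4, 6, 8 and 12. From m = 6 upward this exceeds the artefact it replaces, with the opposite sign.

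**6. Between-arm difference in change, 80 v 20.** Simulated false positives were 3% to 6% in every scenario, which is the nominal level within simulation error.

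**The case against.** The strongest reply is that the artefact is conditional and small. The protocol nowhere says that the screening visit is counted; the GP form is not shown and may settle it. People with long-standing chronic disease seen at routine appointments may attend regularly, and at a common rate the shift is only 0.1 visit. The valid comparison is already a stated objective, and the mixed models on the list could carry it. All of this stands, and it limits the point. It does not remove it: the protocol leaves the windows open, and the synopsis applies paired tests to secondary outcomes, of which consultations are one.

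Several stronger readings are tempting but not supported:

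- A reader might infer that patients are enrolled at the GP visit. They are screened there and consent at the hospital baseline.
- A reader might infer a certain fall of one visit. That is the upper end of the range, and neither size nor sign is fixed.
- A reader might infer that the fall flatters the sponsor's hopes. The hypothesis in section 3.1 concerns health orientation and health outcomes; no direction is given for consultations.
- A reader might infer that frequent attenders dominate the sample. The chance of a visit within 3 months, 1 - e^(-m/4), is 22%, 63% and 95% for m = 1, 4 and 12. Sample composition also depends on how rates are distributed among eligible patients, which is unknown. A steady high rate does not by itself create a change.

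**Conclusion.** The point holds in limited form. As written, the within-arm change in GP consultations cannot be read as an effect of the programme. With baseline-split 12-month windows and 3 to 12 visits a year, the false change lies between about -0.1 and -1.0 visit per participant. Other readings of the windows can turn it positive. These sizes rest on assumed visit rates, steady personal rates and the assumed entry mechanism.

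Only the uncontrolled change in one secondary endpoint is affected. Assignment follows baseline (section 4.3), so both arms pass through the same GP screening and the selection cancels between them. That says nothing about other differences that allocation by matching might leave. It is a minor point for a feasibility study, but cheap to settle before the questionnaire goes out.

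**What to change.** **Section 5.1:** make the between-arm difference in change (programme versus control) the result for consultations. Report within-arm changes descriptively, without a paired test as evidence of impact.

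**Section 3.2 and the GP questionnaire:** use one anchor date per participant and equal 12-month windows before and after it, the same in both arms.

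Do not end the before-period the day before the screening visit; step 5 shows that this can replace a false fall with a false rise. If a within-arm change is shown, the before-period should end before recruitment opened. With random visits at a steady rate the before- and after-counts then both have expectation m. With regular visits at differing rates some distortion can remain, because the after-period still opens shortly after a visit. That is a further reason to keep this figure descriptive.

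**Cost:** a few lines of wording, plus precision. The standard error of the between-arm contrast is √(2m(1/80 + 1/20)) against √(2m/80) within the programme arm, a ratio of √5 = 2.24. For random visits at m = 4, 6 and 12 the 95% half-width is 1.96 × √(0.125m) = 1.39, 1.70 and 2.40 visits. The result will be imprecise with 20 controls, and the report should say so.

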#### 4.3 Study procedures

The study will consist of the following procedures:

- 1. Baseline assessment: Conducted after obtaining informed consent, this includes a blood draw, urine test, completion of questionnaires, and the wearing of a monitoring device (smartwatch).
- 2. Assignment to the experimental or control group: Participants will be matched based on key factors such as gender, age, and chronic conditions. Using these criteria, participants will be assigned to either the experimental group, where they will engage in an artistic or cultural activity, or the control group, where they will receive a free ticket to visit a museum, show, or concert. This matching ensures balanced comparison between the two groups.
- 3. Artistic or cultural prescription assignment: About 3-4 weeks after the baseline assessment, participants will be contacted by a **link worker** who will identify and match them with a suitable **art or cultural activity**. Participants in the control group will receive the free ticket at home.
- 4. **Programme participation:** Participants will begin attending the assigned **cultural or artistic activity**, which is scheduled to take place over upt to 25 sessions, **once per week for 1-2 hours**, over a 6 month period.
- 5. Second assessment (6-month follow-up): Six months after initiating the intervention, participants will undergo a second assessment (first follow-up), which will include a blood draw, urine test, questionnaires, and device wearing. This is also when we will start conducting the qualitative interviews.
- 6. Third assessment (12-month follow-up): Six months after the second assessment, participants will complete a third assessment (long-term follow-up or second follow-up), which will again involve a blood draw, urine test, questionnaires, and device wearing.
- 7. Debriefing: Debriefing will involve providing participants with a thorough explanation of the study's purpose, procedures, and findings both during a phone call and in written form once their involvement is complete. This will include answering any questions they may have, clarifying the use of their data, and offering additional information on the results or conclusions of the study. Participants will also be reminded of their rights, including their right to withdraw any personal data if desired, and they will be given the opportunity to provide feedback on their experience.

Participants will be required to attend all assessments at the Family Medicine Service of the **Ospedale Italiano in Lugano**. Questionnaires will be completed using a tablet. **Nurses and physicians** holding a GCP certificate will be responsible for conducting blood draws, reviewing medications, and overseeing the proper use of wearable devices.

Approximately 3 months will be allocated for recruiting participants, during which general practitioners (GPs) will screen potential candidates for eligibility.

Each participant will be involved in the study for 13 months, which includes:

- 1 month for baseline assessment and assignment to a cultural or artistic activity.
- 6 months for participation in the cultural or artistic activity.
- 6 months of follow-up assessments and optional interviews.

Blood will be collected at baseline, at the 6-month follow-up, and at the 12-month follow-up. The blood samples will be used to measure relevant health markers as part of the study's secondary objectives. Blood samples will be stored securely at the Ospedale Italiano and anonymized with unique participant codes.

Efforts to recruit a diverse sample through multiple GP practices in the Lugano municipality will help mitigate selection bias. To address attrition, participants will be encouraged to attend all study assessments through clear communication and regular follow-up by the research team. Additionally, dropout reasons will be monitored and recorded to help assess and adjust for this bias in the analysis. Standardized protocols for data collection and use of validated tools (questionnaires, devices) will minimize measurement bias. Regular calibration and monitoring of devices will ensure accuracy. Key factors such as sex, gender, age, and pre-existing health conditions will be controlled for in the analysis by matching participants for these variables in the experimental and control groups. Additionally, the study will take into account potential confounding factors by adjusting for them in the statistical analysis models.

